1.1.3 Reporting

Local events requiring expedited reporting, are submitted to the UTSW IRB through the UTSW eIRB and to the SCC DSMC Coordinator. Hardcopies or electronic versions of the eIRB report; the NCI ADEERS, FDA Form #3500A forms, or other sponsor forms, if applicable; and/or any other supporting documentation available should be forwarded to the DSMC Coordinator. The DSMC Coordinator forwards the information onto the DSMC Chairman who determines if immediate action is required. Follow-up eIRB reports, and all subsequent SAE documentation that is available are also submitted to the DSMC Chair who determines if further action is required.

If the event occurs on a multi-institutional clinical trial coordinated by the Cancer Center, the DOT Manager or lead coordinator ensures that all participating sites are notified of the event and resulting action, according to FDA guidance for expedited reporting. DSMC Chairperson reviews all serious adverse events within upon receipt from the DSMC Coordinator. The DSMC Chairperson determines whether action is required and either takes action immediately, convenes a special DSMC session (physical or electronic), or defers the action until a regularly scheduled DSMC meeting.

Telephone reports to:

(Investigator: Insert names and phone numbers for required notifications)

UTSW SCC Data Safety Monitoring Committee Coordinator (if fax report is not available) within 1 working day to [contact].

Written reports to:

(Investigator: Insert names, fax numbers, an addresses for required notifications)

UTSW SCC Data Safety Monitoring Committee Coordinator

Email: [contact]

[contact] or deliver to [name]

1. **Unexpected Adverse Events**

Non-serious adverse events which are classified as both unexpected (in terms of nature, severity and frequency) and possibly related require reporting to the UTSW IRB within 10 working days of PI awareness.

2. **SAEs**

Local serious adverse events (SAEs) require reporting within 2 working days of PI awareness, or as described in the protocol.

3. **Unanticipated Problems**

Unanticipated problems, including those that occur as non-local events, require reporting to the UTSW IRB within 10 working days of PI awareness of the event.

For further guidance for Investigators regarding safety reporting requirements for INDs and BA/BE studies, refer to FDA Draft Guidance document:

<http://www.fda.gov/downloads/Drugs/GuidanceComplianceRegulatoryInformation/Guidances/UCM227351.pdf>

G. **Follow-up**

All adverse events will be followed up according to Good Clinical Practices.

H. **Data and Safety Monitoring Plan**

The UTSW Simmons Cancer Center (SCC) Data Safety Monitoring Committee (DSMC) is responsible for monitoring data quality and patient safety for all UTSW SCC clinical trials. As part of that responsibility, the DSMC reviews all local serious adverse events in real time as they are reported and reviews adverse events on a quarterly basis. The quality assurance activity for the Clinical Research Office provides for periodic auditing of clinical research documents to ensure data integrity and regulatory compliance.

A detailed description of the Data and Safety Monitoring Plan is available in section X of the Clinical Research Office Operations Manual.

The SCC DSMC meets quarterly and conducts annual comprehensive reviews of ongoing clinical trials, for which it serves as the DSMC of record. The QAC works as part of the DSMC to conduct regular audits based on the level of risk. Audit findings are reviewed at the next available DSMC meeting. In this way, frequency of DSMC monitoring is dependent upon the level of risk. Risk level is determined by the DSMC Chairman and a number of factors such as the patient population to be studied; adequacy of the data management system; and procedures to ensure the safety of study subjects based on the associated risks of the study. Protocol-specific DSMC plans must be consistent with these principles. The following examples can be used to begin developing DSMC plans for individual protocols.

- **High risk** examples include Phase 1 studies; Phase II or III studies where the SCC is the DSMC; gene therapy or recombinant DNA studies; and studies in which the investigator holds the IND.
- **Moderate risk** examples include pilot studies and other Phase II or III studies where the SCC DSMC is not the DSMC of record and which involve a non-FDA approved drug.
- **Low risk** examples include Phase II or III studies involving FDA-approved drugs where the SCC DSMC is not the DSMC of record, or trials, which involve non-therapeutic interventions.
- **Exempt** examples include non-interventional studies, which are exempt from audit requirements outlined above.

Multisite Monitoring

Monitoring for multi-institutional studies conducted with SCC as the primary site and coordinating center are the responsibility of the DOT Clinical Research Manager (CRM). The CRM or designee monitors all sub-sites for safety and data quality. The purpose of ongoing data monitoring at sub-sites is to ensure regulatory compliance, adherence to protocol requirements, and patient safety.

Sub-sites will be monitored no less than annually. Monitoring on site is preferred; however, remote monitoring is acceptable where there is not adequate funding for travel. The research documentation for at least 5 subjects is reviewed each time a study is monitored.

Monitoring will include verification of source documentation regarding consent, patient eligibility, investigational treatment, drug accountability, serious adverse events, toxicities, and treatment response. Results of data monitoring of sub-sites will be documented and the results will be made available to the QAC, during trial audit.

SAE's and reportable AE's must be reported to the IRB of the institution in which they occurred, the SCC lead investigators, and the SCC DSMC. The DOT Manager or lead coordinator ensures that the PIs at all of the participating sites and the respective IRBs are notified of the events and resulting action for events which modify the risk of the protocol or which otherwise meet FDA requirements for expedited reporting.

XX. **Data analysis and Statistical Methods**

A. **Study Design and Sample Size**

This is a double arm, open label, Phase II study of pioglitazone in patients with pancreatic cancer. The primary endpoint for the sample size calculation is the adiponectin serum levels change after the pioglitazone treatment, which is the main indicator for insulin response improvement. We are interested in testing the hypothesis that pioglitazone can increase adiponectin by 40% from baseline. The change of adiponectin from baseline was defined as $c=(x_1-x_0)/x_0$, where x_1 is the adiponectin level after treatment, and x_0 is the baseline adiponectin level. So the adiponectin

change is a continuous variable. The null hypothesis is that there is no change of adiponectin level. ($H_0: c=0$). The alternative hypothesis is that the treatment will lead to 40% change of adiponectin from baseline ($H_1: c=0.4$). Assuming that the standard deviation of the change is 0.5, (i.e the standard deviation of c values across population is 0.5), that a sample of 15 patients will provide a power of 82% at a significance level of 0.05 to detect 40% changes from baseline. This sample size calculation was implemented using SAS, and was reproduced using Power and Sample Size (PS) software.

B. *Statistical Analysis Plan*

Biomarkers analyses

Statistical graphical tools will be used to illustrate the biomarker changes over time. Mean and median changes of results for glucose tolerance test, serum adiponectin level test, weight changes, and ECOG performance status will be summarized. Pre-defined cut-offs will be used to dichotomize the patients into with or without insulin response improvement which consists changes in serum adiponectin levels and standard glucose tolerance test. The insulin response improvement rate and 95% exact confidence interval will be calculated.

Tumor response analyses

Complete response rate, partial response rate, objective response rate and progression rate after week 8 with the exact 95% confidence intervals will be provided.

Time to progression

For a given patient, time to progression will be defined as the number of days from the day of registration to the day the patient experiences an event of disease progression (or death). If a patient has not experienced an event of disease progression (or death) at the time of analysis, then the patient's data will be censored at the date of the last available evaluation. Progression-free survival will be summarized using the point estimate of the median time to progression, and the associated 90% confidence interval. Moreover, the proportion of patients who are progression free at 24 months (after entering the study) will be calculated and the 90% confidence interval for this proportion will be constructed. The data will be presented graphically using Kaplan-Meier plots. Additionally, exploratory analysis may be performed including multivariate Cox regression analysis with appropriate baseline characteristics as covariates.

Overall survival

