TZDs have been used in a number of cancer-related settings. In a retrospective study in type II diabetic patients there was a 33% decreased incidence of lung cancer among TZD users compared with nonusers after adjusting for confounder interactions. The risk for colorectal and prostate cancers was not significantly altered [16]. TZDs have been used in the context of liposarcomas. Several studies report a positive impact of a TZD regimen, demonstrating induction of solid tumor differentiation by TZDs in patients with liposarcoma. Other studies in contrast concluded that TZDs are not effective anti-tumoral drugs in the treatment of liposarcomas [17]. Of particular interest are the studies in breast cancer patients. Activation of PPAR γ is associated with anti-proliferative effects on human breast cancer cells in preclinical studies. However, clinical trials using PPAR γ ligands in patients with treatment-refractory metastatic breast cancer failed to show any clinical benefits [18]. In contrast to pancreatic cancers, PPAR γ tends to be highly suppressed in breast cancer cells [19] and as such, these cells not offer high levels of PPAR γ target for the TZDs to act upon. The commonly observed up-regulation of PPAR γ in pancreatic ductal adenocarcinoma [20] may predispose these cells to a high level response to the TZDs.

Preliminary data from UT Southwestern in patients receiving pioglitazone as second line therapy for metastatic pancreatic cancer demonstrated significant TZD response. Among treated patients, the increase in adiponectin levels varied from 50% to three times the baseline. However this study was terminated due to poor accrual. Adequate follow up was not possible due to poor survival of patients, demonstrating selection of terminally ill patients to the protocol. Also the effect on other markers of insulin resistance is not known.

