(MRI will be performed on UT Southwestern and PHS patients ONLY) We propose to evaluate the use of MRI to quantitate changes in a) intratumoral fat deposition in pancreatic cancer and b) visceral/subcutaneous fat distribution in pancreatic cancer patients treated with pioglitazone in this phase II study. To determine intratumoral fat content, we will use a previously described advanced chemical shift-based gradient-echo MRI technique that measures the proton density fat fraction (PDFF) [21]. In addition, MRI will allow quantitative determination of body fat volume in the abdomen e.g. subcutaneous/visceral adipose tissue (SAT/VAT) depots, which have been shown to have an important role in insulin resistance [22, 23]. TZD therapy has shown to increase 'good' SAT and have a concomitant decrease in 'bad' VAT and liver fat in patients with diabetes but has not been studied in patients with pancreatic cancer related weight loss.

MRI examination will be performed on a clinical whole body system (Philips Achieva) at 3.0 Tesla at Rogers MRI Center equipped with a dedicated transmit/receive body coil and images will be interpreted by a dedicated study radiologist,(Department of Radiology). Scan protocol include a preliminary localizing sequence and a 3D multi-echo spoiled gradient echo sequence, with scan parameters optimized for fat quantification as previously described [21].

We propose this study to determine, what is the effect of PPAR γ agonist therapy with pioglitazone on adiponectin levels and markers of insulin sensitivity (fasting glucose, OGTT 0, 2 hour, I/G ratio) in pancreatic cancer patients. In addition we will evaluate the effects of pioglitazone therapy on weight, ECOG functional status, quality of life and disease response.

In order to differentiate pioglitazone related effects from chemotherapy related effects we will enroll a cohort of pancreatic cancer patients for correlative analysis only and will serve as a control arm. These patients will meet all eligibility criteria as detailed above but will not receive pioglitazone. **Pioglitazone**

General: Pioglitazone is one of two currently available PPAR γ agonists on the market. It is sold in the US under the name ActosTM. The other drug in this class on the market is rosiglitazone (AvandiaTM).

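### Does setting no change in adiponectin equal to c = 0 on the percent-change scale bias the primary analysis towards a false increase?

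*Combined protocol and SAP*

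**What the plan says.** Section XX.A (Study Design and Sample Size) makes the change in serum adiponectin the variable for sizing the trial. "We are interested in testing the hypothesis that pioglitazone can increase adiponectin by 40% from baseline", it says, and it defines the variable as a proportion of one baseline value: "The change of adiponectin from baseline was defined as $c=(x_1-x_0)/x_0". The null is given in words and in symbols: "The null hypothesis is that there is no change of adiponectin level. ($H_0: c=0". The alternative is c = 0.4. Variability is specified on the same scale: "the standard deviation of c values across population is 0.5". The result is that "a sample of 15 patients will provide a power of 82% at a significance level of 0.05". Neither the test nor its sidedness is named.

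Section XX.B (Statistical Analysis Plan, Biomarkers analyses) then says what will be done with the data. It lists graphs over time and summaries: "Mean and median changes of results for glucose tolerance test, serum adiponectin level test". It adds the proportion of patients classed as improved by cut-offs, with an exact 95% confidence interval. It lists no hypothesis test of c and no transformation.

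Section VI states the primary objective as describing change in insulin-resistance markers, and Section VIII calls the study a pilot and exploratory. The background section gives the reason for the untreated group: "In order to differentiate pioglitazone related effects from chemotherapy related effects we will enroll a cohort". Section XX.B labels the comparison of arms exploratory.

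**The concern.** A ratio to a single noisy baseline is asymmetric. If baseline and week-8 values merely fluctuate with the same distribution, the mean of x1/x0 is above 1, so the mean of c is above 0 although nothing has happened. Section XX.A nevertheless treats an unchanged level and c = 0 as the same statement.

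If c were tested against 0 with the t-test that the power figure implies, the two tails would be unequal and the excess would be on the side of an increase, the result the trial hopes for. At stake would be a pilot that reports a significant rise in adiponectin somewhat too easily.

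**Working it through.** **1. The plan's own figure.** Inputs from Section XX.A: effect 0.4, SD 0.5, n = 15, significance level 0.05. For a one-sample t-test the noncentrality is (0.4/0.5) × √15 = 3.098, with 14 degrees of freedom and a two-sided critical value of 2.145. Power is 82.1%, which matches the stated 82%. A one-sided test would give 90.3%. The implied test is therefore a two-sided one-sample t-test, but this is an inference from the power figure.

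**2. Size of the possible lean.** The documents give no within-patient variation and no distribution for adiponectin. Assume log-normal ratios. The plan's mean ratio of 1.40 and SD of 0.5 then imply a log-SD of √ln(1 + (0.5/1.4)²) = 0.346 and a log mean of ln 1.4 − 0.346²/2 = 0.276. Let noise make up a share f of that log variance, so that under no change the log-SD is s = 0.346√f, the median ratio is 1 and the mean of c is exp(s²/2) − 1. One million simulated trials of 15 patients per row, with a two-sided 0.05 t-test on c:

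| f | s | mean c | false increase | false decrease | total |
|---|---|---|---|---|---|
| 10% | 0.110 | +0.6% | 3.1% | 2.0% | 5.1% |
| 25% | 0.173 | +1.5% | 3.5% | 1.8% | 5.3% |
| 50% | 0.245 | +3.0% | 4.0% | 1.5% | 5.6% |
| 75% | 0.300 | +4.6% | 4.4% | 1.4% | 5.9% |
| 100% | 0.346 | +6.2% | 4.8% | 1.3% | 6.1% |

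If the whole SD of 0.5 applied without treatment (s = 0.434), the result would be 5.6% up and 6.6% in total. So the mechanism is real under these assumptions.

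**3. How far it depends on them.** With heavy-tailed log ratios (t with 5 degrees of freedom, log-SD 0.11 to 0.434), false increases are 2.7% to 3.9% and total error is 4.7% to 5.2%. With 10 evaluable patients and log-normal ratios (s from 0.110 to 0.346), total error is 5.1% to 5.2%. If c is symmetric and normal about 0, there is no effect.

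**4. The other reading of the null.** Section XX.A pairs c = 0 with c = 0.4 and with an SD of c across the population. That is the notation of a population mean. Take mean c = 0 exactly, with log-normal ratios and log-SD 0.346:

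| test | false increase | false decrease | total |
|---|---|---|---|
| t-test on c | 1.1% | 5.1% | 6.1% |
| t-test on log(x1/x0) | 0.5% | 9.1% | 9.6% |

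The excess now lies against the hoped-for direction, and the log-ratio test, the usual remedy, is the worse calibrated of the two.

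**5. What is actually scheduled.** An error rate needs a test, and Section XX.B lists none for c. Of the planned summaries, the median is unaffected: if x0 and x1 are exchangeable, x1 > x0 is as likely as x1 < x0, so the median of c is 0. The mean carries the bias in the table, at most 6.2 percentage points against a target of 40, or about 15% of it (6.2/40). That maximum requires all the planned variability to be noise. The preliminary data make this unlikely: among treated patients "the increase in adiponectin levels varied from 50% to three times the baseline", so patients probably differ in true response. In the exploratory comparison of 15 treated with 10 control patients the bias cancels: the spurious mean difference is 0.0 points and false increases are 2.1% to 2.4%.

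**6. What the log scale would cost.** At the plan's own alternative the geometric mean ratio is exp(0.276) = 1.32, so the reported effect becomes +32% instead of the stated +40%. Power of the log test at n = 15 is 82% at log-SD 0.346, but with the mean ratio held at 1.4 it falls to 64% at 0.40 and 52% at 0.434.

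**The case for a change.** The strongest case for the concern is that Section XX.A does speak of testing, and that it states the null in words as an unchanged level. Under exchangeable fluctuation, that statement and mean c = 0 are not equivalent, whatever the distribution. False increases exceeded 2.5% under every fluctuation model tried (log-normal, normal, gamma and heavy-tailed). The control comparison cannot be relied on to repair this, because arms are assigned at the investigator's discretion, there are at most 10 controls, and its power for the planned effect is only 47%. A log-ratio analysis would need only a change of wording and would keep 82% power at the plan's own inputs.

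The mathematical point stands, and so does the observation that Section XX.A does not name its test. Neither makes percent change a wrong choice. The verbal null is followed at once by symbols and an SD that describe the mean of c, and the aim is stated as a percentage increase. A sponsor who wants the arithmetic mean percent change is entitled to it. The absence from Section XX.B of a test matching the power statement is a separate matter from the choice of scale.

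**Conclusion.** The concern does not hold. Its figures are correct for one set of assumptions: the null means pure exchangeable fluctuation, ratios are log-normal, noise is 10% to 100% of the planned log variance, and a two-sided t-test is applied to c in 15 patients. The cost is then 0.6 to 2.3 percentage points of extra false increases over the nominal 2.5%, and 0.1 to 1.1 points of total error. The documents do not supply the distribution or the noise share, Section XX.B does not schedule the test, and an equally natural reading of the null reverses the direction of the error.

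For a pilot whose primary objective is descriptive, which reports the median beside the mean, and which expects changes of 40% or more, a possible shift of 0.6 to 6.2 points in the mean does not alter what the trial can conclude. Moving to the log scale would change the quantity estimated and could lose power. That is a legitimate preference, but its absence is not a defect.

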1. Describe change in markers of insulin resistance, including in adiponectin levels standard glucose tolerance test, and serum levels of insulin and glucose in patients with pancreas cancer receiving pioglitazone.

Secondary Objectives

1. To determine the tumor response by RECIST in patients with pancreas cancer receiving pioglitazone.
2. To describe changes in weight in patients with pancreas cancer receiving pioglitazone.
3. To describe changes in ECOG performance status in patients with pancreas cancer receiving pioglitazone.

4. To describe changes in symptoms and quality of life using the FACT-Hep scale, version 4 (see Appendix 4).
5. Compare change in blood biomarkers and MRI between the pioglitazone and control arms.

VII. Endpoints

We will assess the primary and secondary endpoints of the study as follows:

Primary End point

The primary end point will be improvement in insulin resistance markers:

- a. Change in serum adiponectin level. We will obtain serum levels of adiponectin at baseline and after 8 weeks of treatment with pioglitazone.
- b. Changes in standard glucose tolerance test. We will perform the area under the oral glucose tolerance test at baseline and after 8 weeks of treatment with pioglitazone.
- c. Fasting levels of serum glucose and insulin. We will obtain serum levels of fasting glucose and insulin every four weeks in all patients receiving pioglitazone

Secondary End points

- a. Objective response (OR) is the proportion of patients with confirmed complete response (CR) or confirmed partial response (PR) according to the Response Evaluation Criteria in Solid Tumors (RECIST). Progression free survival (PFS) and overall survival (OS) of patients on treatment with pioglitazone.
- b. Changes in weight in patients with pancreas cancer receiving pioglitazone.
- c. Changes in ECOG performance status in patients with pancreas cancer receiving pioglitazone.
- d. Changes in symptoms and quality of life using the FACT-Hep questionnaire, version 4 (see Appendix 4).
- e. Characterize MRI determined changes in a) pancreatic intratumor fat; and b) body fat distribution in pancreatic cancer patients treated with pioglitazone (pilot study on 8-10 patients chosen by PI/investigator discretion) (UT Southwestern and PHS patients ONLY).
- f. Compare changes in serum and MRI end points between pioglitazone and control arms.

VIII. Study Design

Study Arm:

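### Section XX.A sizes the trial on a test of the continuous adiponectin change, but Section XX.B does not carry that test forward, and the 82% power needs all 15 treated patients to supply a pair

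*Combined protocol and SAP*

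**What the plan says.** Section XX.A takes adiponectin change as the endpoint for sample size and announces a test: "We are interested in testing the hypothesis that pioglitazone can increase adiponectin by 40% from baseline". It defines c = (x1 − x0)/x0, calls it continuous, and sets H0: c = 0 against H1: c = 0.4 with SD 0.5. It concludes that "a sample of 15 patients will provide a power of 82% at a significance level of 0.05 to detect 40% changes from baseline". Neither the test nor its sidedness is named.

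Section XX.B, under Biomarkers analyses, turns to description: "Mean and median changes of results for glucose tolerance test, serum adiponectin level test, weight changes, and ECOG performance status will be summarized". It then says "Pre-defined cut-offs will be used to dichotomize the patients into with or without insulin response improvement", with improvement built from adiponectin and the glucose tolerance test, and adds: "The insulin response improvement rate and 95% exact confidence interval will be calculated". No cut-off values or combination rule appear anywhere in the document.

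On timing, XX.A says that x1 "is the adiponectin level after treatment, and" x0 is the baseline level. Section VII is more specific: "We will obtain serum levels of adiponectin at baseline and after 8 weeks of treatment with pioglitazone". Section XIII.F also schedules an adiponectin draw at the early-termination visit. Sections IV and VIII plan 15 pioglitazone patients.

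**The concern.** The sample-size section and the analysis plan address different quantities. XX.A is about the mean of a continuous variable. The only biomarker inference in XX.B is about a proportion of patients, defined by thresholds that are not written down.

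If XX.B is followed as it stands, the question that justified 15 patients is reported without a test or an interval. What is reported with an interval is a rate that depends on unstated cut-offs and has no reference value to be judged against. Treatment is open label and the arm is chosen by the investigator, so thresholds settled after the results are known could move that rate.

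The second issue is the margin. Treated enrolment equals the number in the power statement. Any patient without a usable second sample therefore lowers the power below the quoted figure, and the plan does not say which samples are usable.

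**Working it through.** **Inputs, all from XX.A:** mean c = 0.4, SD = 0.5, alpha = 0.05, n = 15. The standardised effect is d = 0.4/0.5 = 0.8.

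**Reproducing the 82%.** For a two-sided one-sample t-test, power = P(|T| > t(0.975, n−1)), where T is noncentral t with n−1 degrees of freedom and noncentrality d√n. At n = 15 the noncentrality is 0.8 × √15 = 3.098 and the critical value is 2.145, which gives 82.1%. The alternatives fit less well at n = 15: one-sided t 90.3%, two-sided normal approximation 87.3%, one-sided normal 92.7%, and two-sided exact Wilcoxon signed-rank about 80% (simulated, normal c). The quoted figure is therefore best read as a two-sided one-sample t-test of mean c on 15 complete pairs.

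**Power and precision by number of pairs.** The 95% half-width is t(0.975, n−1) × 0.5/√n.

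| Pairs | d√n | t(0.975, n−1) | Power | 95% half-width |
|---|---|---|---|---|
| 15 | 3.098 | 2.145 | 82.1% | 0.277 |
| 14 | 2.993 | 2.160 | 79.0% | 0.289 |
| 13 | 2.884 | 2.179 | 75.4% | 0.302 |
| 12 | 2.771 | 2.201 | 71.4% | 0.318 |

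An observed mean rise of 40% with SD 0.5 would have a 95% interval of 0.400 ± 0.277, about 12% to 68%, at 15 pairs. At 12 pairs it would be 0.400 ± 0.318, about 8% to 72%. XX.B asks for no such interval.

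**Is the test supplied elsewhere in XX.B?**
- The biomarker paragraph gives graphs, means and medians for the continuous change.
- The correlative analyses use adiponectin to explain tumour response and progression-free survival, so they do not test c.
- The comparison with the control arm is labelled exploratory, and it is a different contrast.
- The remaining intervals are for tumour response, progression and survival.

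**Does the 82% transfer to the improvement rate?** Power belongs to a specified test against a specified null. The rate has no null value, no cut-offs and no combination rule, and it includes a glucose component that is absent from XX.A. No power can be attached to it from the plan's inputs.

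**The case against.** The strongest reply is that this is a non-randomised pilot study that calls itself exploratory, and that its primary objective begins "Describe change in markers of insulin resistance". Descriptive summaries fit that objective, and this part of the reply stands. It does not dispose of the point. Section V also hypothesises significant improvement in insulin-resistance markers, and XX.A states a null, an alternative, an alpha and a power. An estimate reported descriptively also needs an interval, and XX.B gives intervals to its other main outcomes.

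A second reply is that XX.A and XX.B belong to one section, so the test in XX.A is already a commitment. This is largely fair. A reader might infer that the trial plans no test at all, but the text does not support that, because XX.A says a hypothesis is to be tested. The defect is that the analysis plan does not name the test or carry it through.

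Two further readings go too far. One is that the 82% is wrong; it reproduces from its own inputs. The other is that it strictly requires 15 week-8 samples. XX.A asks only for a level after treatment, and adiponectin is drawn at early termination, so a patient who stops early but attends that visit might still supply a pair. Section VII favours week 8, but the plan does not settle the matter.

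Nor can the trial be called underpowered on these documents. They give no loss rate, and the ECOG 0–2 limit is meant to reduce early loss. The background section reports that poor survival prevented adequate follow-up in an earlier pioglitazone study, but gives no figure.

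**Conclusion.** The point holds and should be fixed. XX.B omits the analysis on which XX.A justifies the sample size. Its only biomarker interval is on an incompletely defined composite rate to which the 82% does not apply.

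The 82% is correct for 15 baseline/post-treatment pairs, with no allowance for loss. If Section VII governs, these are week-8 pairs, and losing one, two or three takes power to 79%, 75% or 71%.

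These figures rest on XX.A's mean of 0.4 and SD of 0.5, on approximately normal c, and on the two-sided t-test inferred from the match to 82%. No loss rate is assumed.

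**What to change.** 1. In XX.B, make the primary biomarker analysis the test that XX.A was sized on: a two-sided 0.05 one-sample test of mean c in the pioglitazone arm, reported with the estimate and 95% confidence interval. If the SD is 0.5, the expected half-width is about 0.28 at 15 pairs and 0.32 at 12. Ratio changes may be skewed, so a log-ratio or signed-rank analysis can be pre-specified as a sensitivity analysis. Keep the dichotomised rate as descriptive, with its cut-offs and combination rule fixed before data are seen.
2. In XX.A, name the test and its sidedness. State that 82% refers to 15 complete pairs, with 79%, 75% and 71% at 14, 13 and 12.
3. Reconcile XX.A's post-treatment x1 with the 8-week time point in Section VII, and state whether an early-termination sample may serve as x1. That choice is for the trial team.

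The cost is wording in Section XX, with no added patients, visits or samples. The stated power becomes slightly less favourable if pairs are lost.
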